5.4 Treatment Regimen Combination

Patients will be seen in the outpatient office on Day #1 of every cycle and receive administration of ipilimumab and nivolumab or once in maintenance phase nivolumab alone. On Day #2 they will undergo IEMBO consisting of intra hepatic artery administration of GM-CSF (1500mcg) mixed with ethiodized oil emulsion, followed by embolization of the hepatic artery with gelatin sponge particles under the care of interventional radiology. Patients will undergo this combination intervention every 3 weeks for 12 weeks unless significant disease progression, limiting toxicity, or withdrawal of consent. Interim imaging after 2 cycles will be peformed to ensure there has not been rapid progression. After four combination treatments if noted to have CR, PR, or SD patients will be offered maintenance therapy with combination intervention every 4 weeks until disease progression, limiting toxicity, or withdrawal of consent. When undergoing every 4 week maintenance patients will receive NIVO on Day #1 and IEMBO on Day #2 of each 28 day cycle.

5.5 Risks

There may be an increased risk of adverse events such as immune hepatitis or other liver toxicities with the combination therapy than would be seen with each treatment alone. See

section 6.2 for list of comprehensive adverse events and potential risks associated with the treatment.

5.6 Prior and Concomitant Therapy

For immune-related adverse events, steroid treatment will be allowed if it is tapered to 5 mg of prednisone or less before initiation of next cycle. Patients cannot have had prior exposure to anti-CTLA4 or anti-PD1 therapy. They cannot have had prior regional liver directed therapy but may have had liver resection or focal ablation. Palliative radiation is allowed during treatment. Patients who had cellular immunotherapy must have a washout period of at least 90 days prior to first treatment cycle. Patients who had other systemic therapies or radiation treatment must have a least a two week washout period prior to first treatment cycle. Bone strengthening agents such as zolendronic acid or denosumab are also allowed for bone metastases.

6.0 STUDY PROCEDURES

6.1 Study Visit Schedule See Appendix (Section 15.1)

6.1.1 Initial visit

A complete physical examination will be done within the four weeks prior to the initiation of the treatment. The tests and procedures described will be discussed with patients. The detailed treatment procedure and possible side effects will be discussed with patients and verbal and written consent for the treatment will be obtained. The tests and procedures listed below will be ordered after patients sign the consent form. If patients already have had tests performed as part of their standard care, the results of the tests will be recorded.

Once eligibility for the study is confirmed, the embolization procedure will be scheduled through Cardiovascular Interventional Radiology (CVIR).

The following studies and procedures must be performed within 4 weeks of initiation of treatment except pregnancy test (within 2 weeks). All abnormal and normal results must be recorded.

- 1. Medical history to include determination of tumor-related symptoms
- 2. Physical examination to include ECOG performance status, patient height and weight, vital signs.
- 3. Liver biopsy: Core biopsy of the liver tumor to confirm the diagnosis of metastatic uveal melanoma and to evaluate the host response to tumor. A separate standard procedure consent form must be obtained for biopsy of liver tumor.
- 4. Contrast-enhanced CT or MRI of the brain, CT of the chest (without contrast), CT of abdomen and pelvis (with and without contrast), and MRI of the abdomen (with and without contrast)
- Blood tests to include the following:
 Complete blood count (CBC) with differential white blood cell count
 Serum laboratory studies including total bilirubin, SGOT (AST), SGPT (ALT),
 LDH, alkaline phosphatase, albumin, creatinine, BUN, glucose, calcium,
 phosphorus, CRP, PT, PTT, INR, TSH, T3, T4, ACTH and Cortisol
- 6. Pregnancy test (only in women of childbearing potential). The test must be done within 2 weeks prior to initiation of treatment.

6.1.2 Evaluation during treatment

An interim history and physical examination will be performed prior to each subsequent treatment cycle to assess toxicities and disease status. This is to be done upon admission to the hospital and at outpatient appointments for immunotherapy infusion.

CBC with differential, platelet count, liver function tests and renal function tests and LDH will be done prior to the treatment, day of IEMBO, day after IEMBO and, and then weekly unless more frequently is required. In the event that a subject is no longer receiving infusion on Day 1 (IPI and/or NIVO), and only receiving IEMBO – Day 1 labs (CRP, TSH, & T4) will be drawn prior to IEMBO on Day 2.

Due to possibility of abrupt onset endocrinopathy TSH,ACTH, T3, T4, cortisol will also be ordered as part of monitoring for side effects related to IPI+NIVO and NIVO the week prior to scheduled infusion. On Day 1 of each cycle TSH and T4 will also be ordered.. Lipase will be ordered on as needed basis.

Coagulation tests (PT, PTT, INR) will be done prior to each embolization.

Sixty (60) ml of blood will be drawn for immunological testing prior to each cycle beginning. Additionally, 10 ml of blood will be drawn before, 1 hours and on Day 3 after the individual IEMBO for cytokine measurements. Also up to an additional 10ml of blood will be drawn prior to the initial cycle for purposes of determining tumor mutational load. Study blood will be collected for the first 6 cycles of treatment, then at 12 and 24 months and at End of Treatment visit, even if visit is before the completion of 6th cycle.

Eligibility criteria will be applied to each treatment. Only the patients who fulfill the eligibility criteria will be offered further embolization treatment. If follow-up test results indicate that patients have become ineligible for treatment, the next treatment will be postponed for a maximum of 4 weeks. If sufficient improvement is not seen during this period to restore eligibility for the next treatment, they will be removed from the study.

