Methodology/Study Design	Open label, prospective, Phase II single arm trial. Patients will receive immunoembolization (IEMBO) every 3 weeks in combination with ipilimumab (IPI) + nivolmuab (NIVO) initially to be given every 3 weeks for 4 doses. Dose of IPI + NIVO will be the reverse lower dose of IPI 1mg/kg every 3 weeks x4 doses and NIVO 3mg/kg every 3 weeks x 4 doses then NIVO flat dose 480mg every 4 weeks. In the event of toxicity during the first four IPI + NIVO + IEMBO combination treatments, IPI and/or NIVO may be dropped at the investigator's discretion and patient can continue on with NIVO + IEMBO or IEMBO alone. Once patient completes the first four doses of combination and moves onto the maintenance NIVO phase, IEMBO will then be given every 4 weeks. In the event of NIVO-related toxicity during this phase, NIVO can be dropped at the investigator's discretion. Initial scans will be performed following two IPI+NIVO and IEMBO treatments, before treatment #3, to ensure no evidence of rapid progression. Initial radiographic response will be determined following all 4 doses of IPI+NIVO and/or NIVO alone if IPI dropped and/or four IEMBO treatments if both IPI and NIVO are dropped. Subsequent scans will be done every two IEMBO treatments. Immune-related side effects will be managed as per protocol. Steroid treatment will be allowed if it is tapered to 5 mg of prednisone or less before initiation of next cycle. Combination treatment could be postponed for up to 10 weeks (from the date of next scheduled treatment). if patients need a treatment break for immune-related toxicity. Safety will also be assessed and the toxicity of the treatment will be monitored using the NCI Common Toxicity Criteria. Immunologic parameters will also be evaluated as detailed in the protocol.
Study Duration	18-24 months to accrue. Subjects will receive study treatment for a maximum of 2 years and will subsequently be followed for a minimum of one year.
Study Center(s)	Thomas Jefferson University Hospital

	Primary Objective: Determine the clinical benefit of combination treatment with IEMBO, Ipilimumab, and Nivolumab.			
Objectives	Secondary Objective(s): 1. Determine all treatment and immune related toxicities 2. Determine PFS 3. Determine OS Exploratory Objective:			
	Determine and correlate clinical response with the degree and change in inflammatory/immune response			
Number of Subjects	35			

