3.0 STUDY DESIGN

3.1 General Design

This study is an open label, prospective, phase II, two-stage, single arm trial with the potential for improved outcome with treatment of IEMBO in combination with IPI + NIVO. Patients will receive study treatment for a maximum of two years or until disease progression. The design will be a two-stage minimax design using the method of Simon. Choice of design is guided by a desire to stop the trial early if the actual hepatic metastasis stabilization rate is 60% or less. If the stabilization rate rate is 80% or greater, we would like to have a low probability of failing to conclude effective.

Patients will receive IEMBO every 3 weeks in combination with IPI + NIVO initially to be given every 3 weeks for 4 doses. Dose of IPI + NIVO will be the reverse lower dose of IPI 1mg/kg every 3 weeks x4 doses and NIVO 3mg/kg every 3 weeks x 4 doses then NIVO flat dose 480mg every 4 weeks. In the event of toxicity during the first four IPI + NIVO + IEMBO, IPI and/or NIVO may be dropped at the investigator's discretion and patient can continue on with NIVO + IEMBO or IEMBO alone. Once patient completes the first four doses of combination and moves onto the maintenance NIVO phase, IEMBO will then be given every 4 weeks. In the event of NIVO-related toxicity during this phase, NIVO may be dropped at the investigator's discretion and the patient may continue on with IEMBO only, if the investigator feels patient is receiving clinical benefit from it. Initial scans will be performed between cycles 2 and 3 to ensure no evidence of rapid progression. Initial radiographic response will be determined following all 4 doses of IPI+NIVO and/or NIVO alone if IPI dropped, and/or four IEMBO treatments if both IPI and NIVO are dropped. Subsequent scans will be done after every two IEMBO treatments. Immune-related side effects will be managed as per protocol. Steroid treatment will be allowed if it is tapered to 5 mg of prednisone or less before initiation of next cycle. Combination treatment could be postponed for up to 10 weeks (from the date of next scheduled treatment), if patients need a treatment break for immune-related toxicity. Safety will also be assessed and the toxicity of the treatment will be monitored using the NCI Common Toxicity Criteria. Immunologic parameters will also be evaluated as detailed in the protocol.

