4.0 SUBJECT SELECTION AND WITHDRAWAL

4.1 Inclusion Criteria

- Histologically confirmed metastatic uveal melanoma in the liver. Patients must have at least one measurable liver metastasis that is ≥ 10 mm in longest diameter by CT scan or MRI.
- 2. The total volume of the tumors must be less than 50% of the liver volume.
- 3. Willingness and ability to give informed consent.
- 4. Agreement to access archival tissue or agreement for tumor biopsy prior to treatment
- 5. ECOG performance status of 0, or 1
- 6. Adequate renal and bone marrow functions: serum creatinine ≤ 2.0 mg/dl, granulocyte count ≥ 1000/mm3, and platelet count ≥ 100,000/mm3.
- 7. Adequate liver function: bilirubin ≤ 2.0 mg/ml, albumin ≥ 3.0 g/dl, PT/PTT less than 1.5 times normal, AST and ALT less than 3x ULN and alkaline phosphatase less than 1.5 times ULN (grade 1).
- 8. Age \geq 18 years of age.
- 9. Women must not be pregnant or breast-feeding. See section 4.2.1
- 10. Women of child-bearing potential must use at least two other accepted and effective methods of contraception and/or to abstain from sexual intercourse for at least 23 weeks after the last dose of nivolumab and/or ipilimumab and sexually active males must use at least two other accepted and effective methods of contraception and/or to abstain from sexual intercourse for at least 31 weeks after the last dose of nivolumab and/or ipilimumab. See section 4.2.1

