6.3 Dose Delays and Dose Modifications

6.3.1 Attributed to Immunoembolization with GM-CSF

If CTC Grade 4 systemic and or local toxicities related to GM-CSF are observed, no further dose will be offered, with the exception of Grade 4 AST/ALT elevation as long as resolves within 7 days.

6.3.2 Attributed to Ipilimumab, Ipilimumab or Nivolumab, or Nivolumab alone. See Appendix 3 for management of immune related toxicities.

6.3.3 Attributed to combination of Ipilimumab and Nivolumab and Immunoembolization or Nivolumab and Immunoembolization

Combination treatment could be postponed for up to 10 weeks (from the date of next scheduled treatment). if patients need a treatment break for immune related toxicity. During combination treatment with IPI and NIVO, depending on type and severity of toxicity, patient may be able move onto the maintenance phase of NIVO + IEMBO and drop the IPI before the full four combination doses are given. Likewise, NIVO may also be dropped and patient may be able to continue on with IEMBO only, if the investigator feels patient is receiving clinical benefit from it. These determinations may be made at the investigator's discretion, in consideration of patient safety.

A window of +/- 3 days is permitted between each treatment cycle beginning at cycle 2 and will not be characterized as dose or treatment delay.

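### Sections 6.1.2 and 6.1.6 remove a patient whose tests stay ineligible after a 4-week postponement, 6.3.3 allows 10 weeks for immune-related toxicity, and no readable text says which rule governs immune hepatitis

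*Combined protocol and SAP*

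**What the plan says.** **The 4-week rule.** Section 6.1.2 applies the eligibility criteria at every treatment: "Only the patients who fulfill the eligibility criteria will be offered further embolization treatment". It continues: "If follow-up test results indicate that patients have become ineligible for treatment, the next treatment will be postponed for a maximum of 4 weeks", and then: "If sufficient improvement is not seen during this period to restore eligibility for the next treatment, they will be removed from the study". No cause is exempted. Section 6.1.6 lists failure of the eligibility criteria for the combination as a ground for removal, with neither a time limit nor an exception.

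**The 10-week rule.** Section 3.1 says of the combined regimen that it "could be postponed for up to 10 weeks (from the date of next scheduled treatment), if patients need a treatment break for immune-related toxicity". The Study Summary (Methodology/Study Design) has the same allowance, and the dose-delay text in 6.3.3 repeats it: "Combination treatment could be postponed for up to 10 weeks (from the date of next scheduled treatment", again for immune-related toxicity.

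**Where they meet.** Inclusion criterion 7 in 4.1 requires "AST and ALT less than 3x ULN and alkaline phosphatase less than 1.5 times ULN (grade 1". Exclusion 1 in 4.2 turns any failed inclusion criterion into an exclusion. Section 6.2 names hepatitis among the immune-related events, and 5.5 warns that the combination may raise the risk of immune hepatitis.

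**Who is counted.** Section 7.2.1 limits the evaluable population to patients with at least four treatments and the assessment after them. Section 4.3.3 replaces patients withdrawn before the fourth-cycle assessment unless the reason is clinical deterioration or toxicity. Section 9.1 treats a patient as evaluable for clinical response after one IEMBO.

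**The concern.** The liver is both the treated organ and the organ most likely to trigger the conflict. Section 6.1.2 requires weekly liver tests, so a rise in AST/ALT to 3x ULN or more will be seen. If it is immune-mediated, one section requires removal after 4 weeks and another permits waiting 10. Two investigators following the same protocol could treat the same patient differently.

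Before the fourth treatment, that choice decides whether the patient reaches the primary assessment. It then runs into a second gap. A treated patient removed early for toxicity is outside the evaluable population by 7.2.1, is not replaced by 4.3.3, and is evaluable by 9.1. If 7.2.1 is followed, patients who left because of toxicity drop out of the denominator and the hepatic stabilization rate is pushed upward.

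**Working it through.** The plan gives no figure for this point, so the main check sets the texts side by side. The two-stage design itself (13 then 35 patients, stop at 8 or fewer, reject at 26 or more) is not in question. Exact binomial sums give type I error 0.0499 at 60%, power 0.808 at 80% and early-stopping probability 0.647 at 60%, in line with 7.2.

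**1. Do both rules apply to one event?**

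| | 6.1.2 (and 6.1.6) | Study Summary, 3.1, 6.3.3 |
|---|---|---|
| Trigger | Follow-up tests fail eligibility | Immune-related toxicity |
| Limit | 4 weeks (6.1.6: none given) | 10 weeks from the next scheduled treatment |
| At the limit | Removal from the study | Not stated |
| Exception or cross-reference | None | None |

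Immune hepatitis with AST/ALT at or above 3x ULN satisfies both triggers. Immune toxicity that fails no test criterion, such as colitis with acceptable laboratory values, satisfies only the second and is outside the conflict.

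**2. Does other text settle it?**

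- Dropping IPI and NIVO and continuing IEMBO alone (6.3.3) does not, because 6.1.2 offers further embolization only to patients who meet the criteria.
- Section 6.3.1 does not. It stops dosing for grade 4 toxicity related to GM-CSF, "with the exception of Grade 4 AST/ALT elevation as long as resolves within 7 days". That is a limit by cause, but for a different cause and a much shorter time.
- The readable note to the hepatic algorithm in 15.3 permits delay instead of discontinuation below 8x ULN for AST/ALT but gives no duration. The body of that algorithm is a figure that could not be read.

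**3. How wide is the gap?** The limits are 4 x 7 = 28 days and 10 x 7 = 70 days, a window of 70 - 28 = 42 days. With treatments every 21 days from day 1, and assuming that the 4 weeks also run from the due date (6.1.2 names no starting point):

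| Treatment | Due day | Latest day, 6.1.2 (+28) | Latest day, 6.3.3 (+70) |
|---|---|---|---|
| 2 | 22 | 50 | 92 |
| 3 | 43 | 71 | 113 |
| 4 | 64 | 92 | 134 |

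**4. How many patients?** The documents do not say. For scale only, Table 15.2-2 (IPI+NIVO without embolization) lists:

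- autoimmune hepatitis, 1.22%: 35 x 0.0122 = 0.4 patients
- serious ALT increase, 2.77%: 35 x 0.0277 = 1.0 patient
- any ALT increase, 11.50%: 35 x 0.1150 = 4.0 patients

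None of these is defined by 3x ULN or by a duration of 28 to 70 days. By 5.5 the risk with embolization may be higher. They are neither estimates nor bounds.

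**5. What does the denominator do?** Take one treated patient removed for toxicity before the assessment, not replaced, and 26 successes among the others. Counted as a non-success, the rate is 26/35 = 74.3%. Left out under 7.2.1, it is 26/34 = 76.5%. The difference is 2.2 percentage points per such patient.

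**The case against.** The best defence is that a specific rule governs a general one. The 10-week limit appears three times, is confined to immune-related toxicity and sits in the dose-delay section. The readable gastrointestinal and endocrine algorithms call for steroid tapers of at least a month, which fits 10 weeks far better than 4. Nor can 6.1.2 mean mechanical re-application of every criterion: exclusions 2 and 3 (prior checkpoint antibody, prior liver-directed treatment) would then bar everyone at cycle 2. This largely stands. It makes the 10-week reading the likelier one and lowers confidence that sites would go wrong. It does not remove the conflict, because AST and ALT are exactly the follow-up test results that 6.1.2 is about.

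Exclusion 12 sets 5 times normal for active hepatitis, which might seem to displace the 3x limit. Exclusion 1 keeps inclusion 7 in force. Even if only the 5x limit were re-applied, the overlap would narrow, not vanish. The unread hepatic figure is a fair reason for caution: it might contain a duration.

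The denominator problem exists for any early toxicity withdrawal, whichever delay limit applies. That is true, so it is presented as a linked fix and not as a consequence of the 4-versus-10-week conflict alone.

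Two stronger readings are tempting and not supported:

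- A reader might infer a loss of power or an inflated type I error. A power loss needs the removed patient to be a certain non-success while all others keep an 80% rate; if the 80% target already allows for such failures, nothing is lost. An inflated type I error needs the cut-off lowered to 25 of 34, which no document proposes. With 26 kept, type I error falls.
- A reader might infer that exclusion 10's 4-week immunosuppression window conflicts with the steroid rule. That window is not a test result, and 5.6 already gives the on-study rule of 5 mg prednisone or less before the next cycle.

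**Conclusion.** The concern holds as an unresolved conflict between operative sections. For immune hepatitis with AST/ALT at or above 3x ULN that needs between 28 and 70 days to recover, literal use of 6.1.2 and 6.1.6 removes a patient whom 6.3.3 would allow to stay. The 10-week rule is probably what is meant, but no readable text says so. The linked gap also holds: 7.2.1 leaves unreplaced toxicity withdrawals out of the primary denominator, against 9.1, and that moves the observed rate upward.

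The effect is minor. The number of patients affected is unknown and probably small. Confidence is moderate, because the conclusion assumes that 6.1.2 covers laboratory criteria such as AST/ALT and that the hepatic algorithm figure gives no overriding duration.

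**What to change.** **Delay rule.** In 6.1.2 and 6.1.6, state that the 4-week limit applies except for immune-related toxicity managed under 6.3.3, where the limit is 10 weeks from the next scheduled treatment. The patient would still have to meet the test criteria before re-embolization. If the sponsor considers 10 weeks unsuitable for re-embolization, set one common limit in all the sections concerned.

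**Analysis rule.** In 7.2.1, consistent with 4.3.3 and 9.1, state that a treated patient removed for toxicity before the four-treatment assessment counts as a non-success, both among the first 13 and among the 35.

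**Cost.** A few sentences in one amendment, with no extra patients. One break of the maximum length moves that patient's four-treatment scan from week 12 to as late as week 22. The analysis rule gives a slightly lower observed rate (74.3% instead of 76.5% in the example above), and lower power if the 80% target did not already allow for such failures. The sponsor should say whether it did.

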6.1.3 Post-embolization liver biopsy

Three weeks after the first embolization and prior to the second embolization, the second liver biopsy will be performed to evaluate the host response to tumor *if technically feasible*. A separate standard procedure consent form must be obtained for biopsy of the liver tumor.

6.1.4 Office visit after 4 cycles

After the fourth cycle patients will be evaluated for response. The tests and procedures described below will be performed.

- 1. Medical history to include determination of tumor-related symptoms
- 2. Physical examination to include ECOG performance status, patient height and weight, vital signs
- 3. CT of the chest (with contrast), CT of abdomen and pelvis (with and without contrast), and MRI of the abdomen (with and without contrast)
- 4. Blood tests to include the following

Complete blood count (CBC) with differential white blood count. Serum laboratory studies including total bilirubin, SGOT, SGPT, LDH, alkaline phosphatase, albumin, TSH, creatinine, BUN, glucose, calcium, and phosphorus. Sixty (60) ml of blood will also be drawn for immunological testing.

After the completion of 4 treatments, continuation of the treatment will be offered to patients who have demonstrated clinical benefit from the treatment and have not experienced any CTC grade 4 toxicity while participating in this study. If the patient started with unilobar disease but develops liver metastases in the contralateral lobe treatment to the contralateral lobe with immunoembolization and continuation of the treatment will be allowed.

If patients have progression of liver metastases, or progression of extra-hepatic metastases that require a change in systemic therapy (palliative radiation or surgery allowed as per discretion of investigator) determined by RECIST 1.1, or experienced serious side effects, patients will be removed from the study and appropriate medical advice regarding alterative treatment options will be provided (See Section 6.1.6 Completion of the study).

If patients have unequivocal progression of hepatic metastasis prior to the visit after 4 treatments, they may be removed from the study at the discretion of the investigators and appropriate medical advice will be provided. In that case, patients will be followed every 3 months to document their medical condition until their death. Follow-up over the telephone will be performed for patients unable to return for examination. If there is a mixed response seen at the interim scan completed between cycles 2 and 3, and it is deemed patient is getting clinical benefit, they will be allowed to continue with study treatment.

If patients have stabilization of hepatic metastasis but progression of extra-hepatic metastasis after 4 treatments, two additional IEMBO treatments, 4 weeks apart, will be allowed as long as hepatic metastasis is stable. This would prevent the early removal of patients with pseudo-progression of extra-hepatic metastasis. If follow-up imaging studies show further progression of extra-hepatic metastasis after 2 additional IEMBO + NIVO treatments, patients will be removed from the study. In that case, patients will be followed every 3 months to document their medical condition until their death. Follow-up over the telephone will be performed for patients unable to return for examination.

After the completion of first four treatment cycles, if disease stabilization is determined (at 12 weeks), continuation of treatment on maintenance phase may be offered as a combination of IEMBO +NIVO or, in the event of NIVO-related toxicity, IEMBO alone.

6.1.5 Additional outpatient visits prior to infusion of IPI+NIVO or NIVO alone. Patients will be seen in the outpatient setting prior to each infusion of IPI+NIVO or NIVO alone during maintenance.

During maintenance phase, after the completion of every two treatments patients will be seen by both medical oncology and interventional radiology for evaluation. A complete physical examination will be done by a study physician.

CT scan of the chest (with contrast), CT of abdomen and pelvis (with and without contrast) and MRI of the abdomen (with and without contrast) will be obtained prior to the subsequent follow-up office visits after every two treatments (NIVO + IEMBO).

The decision to continue treatment will be based on the results of the imaging and laboratory tests and the physical status of the patients. Unless patients become ineligible based on the inclusion/exclusion criteria, or unless patients develop rapid progression, or unless patients experience an unacceptable serious adverse event, the combination treatment will be continued.

Patients who experience progressive disease by RECIST criteria without clinical deterioration may continue on protocol therapy until their next scheduled scan if the investigator feels the patient may be having clinical benefit and may experience a delayed or atypical response. Only patients who have no progression of symptoms of cancer, no decline in performance status, and no progression of tumor at a critical anatomic site (e.g., cord compression) will be eligible for the treatment beyond progression. If the next scheduled scan shows a further increase in tumor measurements (>10% RECIST target lesions or unequivocal progression of non-target lesions) from the scan that first suggested progression, patient will be deemed to have true progression and patient will be removed from study. It the next scheduled scan does not show further progression, patient will remain on study treatment.

For patients who achieved PR, CR, or SD in the liver metastases after embolization, tumor measurements should be continued after every 2 IEMBO treatments for up to 2 years after initiation of protocol therapy or until PD is confirmed.

